### Consent Process

1. Describe the consent process; including who will be approached for consent and what type of consent will be obtained from each subject population, if there is more than one.  
**A written consent using the IRB consent template will be used for each new patient undergoing implant-based breast reconstruction. Consent will be obtained by any of the staff included in the IRB application at the initial pre-operative appointment ranging from one week to one month pre-op. Written consent will then be obtained and stored in the medical record.**

### Inclusion/Exclusion Criteria

1. List the inclusion and exclusion criteria.  
**Inclusion criteria:**  
**Patients undergoing first stage breast reconstruction at the University of Missouri.**  
**Age range: 18 years of age and older.**  
**Exclusion criteria:**  
**Patients may not have any existing wounds, nor any existing infections related to an implant device.**
2. Describe restrictions on participation and appropriate screening procedures to ensure that the restrictions are maintained, including pregnancy testing.  
**Restrictions will be any patient's that have any existing wounds or infection or have been on antibiotics within in the past ten days.**

### Number of Subjects

1. Include anticipated enrollment number in this study. Include a break-down in numbers if there is more than one subject population.  
**Our goal is to achieve an  $n$  of 100 with 50 patients allocated to the experimental arm (showering at 48hrs) and 50 allocated to the control (current standard of care).**
2. Include statistical analysis or other justification for the number of subjects enrolled.  
**An  $n$  of 100 provides us with adequate power for a statistically significant difference between subject arms to be detected if one is present.**

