### Research Objectives/Background

1. Include primary, secondary, and exploratory objectives.  
**Primary goal: to evaluate whether allowing showering after a certain number of days post breast reconstruction has an effect on the infection rate**  
**Secondary goal: to evaluate whether allowing showering after a certain number of days post breast reconstruction has an effect on the quality of life of patients**
2. Include background and rationale for initiating the study. Includes pre-clinical and clinical data, current experiences with procedures, drug, or device, and any other relevant information to justify the research.  
**Currently, there is a lack of consensus on best practices regarding showering with drains in place following first stage breast reconstruction. There is anecdotal concern for an increased risk of Surgical Site Infection (SSI), but the current literature to support this is lacking. There is also some evidence that showering with drain tubes in place has no increase risk of infection. It is not known whether showering with drain tubes decreases the risk of SSI. Surgical drains can remain in place upwards of two to three weeks in the postoperative period. The recommendation not to shower until drain removal can present a significant challenge for patients resulting in distress and decreased quality of life. Our study will assess the infection rates in patients allowed to shower at 48 hours postoperatively compared to those not showering until drains are removed. Our hypothesis is that this study will reveal no difference in the rates of SSI and improved quality of life in patients who are allowed to shower with drain tubes in place.**

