### Study Procedures/ Design/Treatment Plan

1. Include study procedures/design/plan; include the sequence and timing of study procedures (distinguish research procedures from those that are part of routine care). Include study duration and number of study visits required.  
**Study will last 90 days. Patient's will be admitted to the hospital following surgery if the reconstruction takes place immediately following mastectomy. If the reconstruction does not occur at the same time as mastectomy, patients are not admitted. This is part of our routine care. Regardless, they will be evaluated on post operative day one. Following the initial post operative day one visit, patient's will be evaluated on a weekly basis for 90 days. Vitals will be taken at the visits, and routine physical examination (including evaluation for surgical site infection) will be performed. Patient reported outcomes will be obtained at these visits as well. We will also ask patients if they have been showering or not and if so how often. This will be documented. For example: patient evaluations will be as follows:**
  - One-month preoperative visit
  - Day of surgery
  - Post Operative Day one evaluation (In the hospital or clinic)
  - Clinic Visit 1: One week after surgery
  - Clinic Visit 2: Two weeks after surgery

**These visits will not differ from our routine care. At the conclusion of 90 days patients will receive a survey asking if drain care and the ability or inability to shower with drain tubes in place adversely affected their quality of life.**

2. Blinding, including justification for blinding or not blinding the trial. Describe unblinding procedures.  
**The study will not be blinded. Participants will be randomly assigned to treatment arm. Researchers and patients will know which arm they are assigned to.**
3. Justification of why participants will not receive routine care or will have current therapy stopped.  
**The goal of the study is to determine if there an effect on infection rate with allowing patients to begin showering 48 hours after surgery rather than waiting to shower until drains are removed. There is no definitive literature on this, and the care of surgical drains is ultimately decided by the surgeon. There is currently no defined standard of care regarding showering with surgical drains in place.**

4. Definition of treatment failure or participant removal criteria.  

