**Removal criteria: failure to shower within 48 hours (experimental arm) or showering before surgical drain removal (Control group). Other removal criteria will be participants that have violated the post operative instructions in any way.**
5. Description of what happens to participants receiving therapy when study ends or if participation in the study ends prematurely.  
**At the end of the study or if patients choose to withdraw prematurely from the study, patients will continue to follow up at designated intervals for general postoperative monitoring.**
6. Include sub-studies or banking information (correlative/special studies)  

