**Data must be kept for seven years after the study has been completed.**

### Potential Risks/Adverse Events

1. Describe reasonably foreseeable risks or discomforts to the subjects and steps to minimize risks.  
**The study involves minimal risks and steps will be taken to mitigate these risks. Risks include: soft tissue infection, breast implant infection, decreased quality of life, breach of confidentiality. Infection risk may be higher, lower, or the same in those who allowed to shower with drains in place compared to those not allowed to shower. There is a lack of literature to support increased risk of infection with showering with JP drains in place. Timing of showering is ultimately surgeon dependent. Regardless, this risk will be mitigated by continuing with sterile surgical technique with proper prepping and draping of the patient as well as sterile placement of drain tubes intra-operatively. Patient's will also be instructed to not soak in water, such as in a bath tub. Rather, they will be instructed to shower and let water run over the drain tube sites. Patients will be immediately treated if there any signs of infection. In terms of decreased quality of life, patients who will not be allowed to shower until drain tubes are removed will be allowed to sponge bath to help mitigate any discomfort. The final risk is possible breach of confidentiality. These risks will be minimized by de-identification of data collected on a separate file, a link between randomly assigned number and identifiable data will be listed. All data collected will be secured on a password protected excel spreadsheet. No persons outside those listed. Accidental removal of a surgical drain is not increased by this study. It is part of our routine care to suture the drain tubes to the skin. Accidental dislodgement of drains is an extremely rare event and is part of the normal post operative surgical risks.**
2. Describe any stopping rules.  
**We would immediately withdraw patients per their request. We would also stop the study all together if there was a clear statistical benefit in one of the study arms.**
3. Include the plan for reporting unanticipated problems or deviations. This plan must include a five-day reporting requirement to the IRB once becoming aware of an event.  

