### **Anticipated Benefits**

1. Include both direct and indirect benefits for either the individual or society.  
**Direct benefits include better understanding factors that contribute to SSI in the postoperative period following first stage breast reconstruction. Indirect benefits include the ability to change current standard practice regarding showering with drains to improve patient quality of life.**

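### The protocol says 100 patients give adequate power to detect a difference if one exists; for surgical site infection, 50 per arm can reliably detect only a very large one

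*Protocol*

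**What the plan says.** Item 1 of Number of Subjects sets a total of 100, with "50 patients allocated to the experimental arm (showering at 48hrs) and 50 allocated to the control (current standard of care"). Item 2, which asks for the justification, answers in a single sentence: an n "of 100 provides us with adequate power for a statistically significant difference between subject arms to be detected if one is present". No endpoint, control rate, effect size, significance level or power figure accompanies it.

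The outcome that matters most is clear from elsewhere. Research Objectives/Background lists "Primary goal: to evaluate whether allowing showering after a certain number of days post breast reconstruction has an effect on the infection rate", and item 3 of the Study Procedures section repeats the aim: "The goal of the study is to determine if there an effect on infection rate". The expected result is also stated: "Our hypothesis is that this study will reveal no difference in the rates of SSI". Potential Risks/Adverse Events leaves the direction open: "Infection risk may be higher, lower, or the same in those who allowed to shower with drains in place". Among the indirect benefits, Anticipated Benefits names "the ability to change current standard practice regarding showering with drains to improve patient quality of life".

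**The concern.** The sentence asserts a property of the design, so the problem is more than missing detail. No fixed sample size has adequate power for every difference that might exist, and 50 per arm is small for a binary outcome that may be uncommon. The question is how far the claim is from the truth for SSI.

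The stakes come from the hypothesis. The investigators predict no difference in SSI and hope the results can change practice. A non-significant comparison is therefore the result they expect. A reader who trusts the power statement would take that result as good evidence that showering with drains does not affect infection. If power is low for differences that would matter, the reassurance is unfounded, and the protocol itself lists soft tissue and implant infection among the risks.

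**Working it through.** **What can be reproduced.** The figure of 100 cannot be, because the protocol gives no inputs that lead to it. The check therefore asks what 50 per arm can detect.

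**Inputs from the protocol**
- 50 patients per arm (Number of Subjects, item 1).
- SSI as a yes/no outcome per patient, compared between arms (Research Objectives/Background).
- Risk may move in either direction (Potential Risks/Adverse Events), which makes a two-sided test the natural reading.

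**Assumptions, none of them in the protocol**
- Two-sided 5% significance level.
- Control SSI rate p0 of 5, 10, 15 or 20%.
- All 50 per arm analysed.
- Fisher's exact test or uncorrected Pearson chi-square.
- A doubling as the illustrative effect.

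**Method.** With a and b infections in the two arms, power is the sum of Bin(a; 50, p0) × Bin(b; 50, p1) over all tables (a, b) for which the test gives p ≤ 0.05. This is exact; no normal approximation is involved.

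| Control SSI rate | 5% | 10% | 15% | 20% |
|---|---|---|---|---|
| Power, doubling, Fisher | 6.3% | 19.5% | 35.4% | 51.5% |
| Power, doubling, chi-square | 14.5% | 30.3% | 44.3% | 59.5% |
| Smallest rise with 80% power, Fisher (points) | 21.4 | 24.4 | 26.4 | 28.0 |
| Smallest rise with 80% power, chi-square (points) | 18.4 | 22.1 | 24.4 | 26.0 |
| Power, complete elimination, Fisher | 3.8% | 38.4% | 78.1% | 95.2% |
| Power, complete elimination, chi-square | 24.0% | 75.0% | 95.4% | 99.4% |
| Smallest fall with 80% power, Fisher (points) | none | none | none | 18.3 |
| Smallest fall with 80% power, chi-square (points) | none | none | 14.0 | 16.8 |

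**One cell by hand.** With no infections in one arm, Fisher's test needs at least 6 of 50 in the other to reach p ≤ 0.05. At a control rate of 5% the chance of 6 or more is 3.8%, which is the Fisher power for complete elimination in the first column.

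**Where a doubling becomes detectable.** Power for a doubling first reaches 50% at a control rate of 16.9% (chi-square) or 19.6% (Fisher), and 80% at 26.9% or 29.0%.

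**Cross-check by sample size.** The pooled normal formula is n per arm = [1.96·√(2p̄(1−p̄)) + 0.8416·√(p0(1−p0) + p1(1−p1))]² / (p1 − p0)², where p̄ is the mean of p0 and p1. For 10% against 20%: [1.96·√0.255 + 0.8416·√0.25]² / 0.01 = (0.990 + 0.421)² / 0.01, or 199 per arm. For a doubling from 5, 15 or 20% the formula gives 435, 121 or 82. All exceed 50.

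**Precision.** With both arms at the control rate, the Wald 95% half-width for the risk difference is 1.96·√(2·p0(1−p0)/50) = 8.5, 11.8, 14.0 or 15.7 points.

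**Removals.** Item 4 of the Study Procedures section removes patients for "failure to shower within 48 hours (experimental arm) or showering before surgical drain removal (Control group"), but does not say that they leave the analysis. If they did and 40 per arm remained (an assumed number), the rise needed for 80% power would be 21–24, 25–28, 28–30 or 29–32 points (chi-square to Fisher).

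**The case against.** The best defence is that the numbers above are not the protocol's. It states no SSI rate, level, test or target effect, and nothing in it makes a doubling the relevant difference. Power is sensitive to these choices: for a doubling it runs from 6% to 60% across the range, and at a 25% control rate it reaches 67% (Fisher) or 75% (chi-square). The inputs might stand in a separate statistical analysis plan. The protocol also nowhere says that a non-significant result will be read as equivalence, and the benefit it lists is framed in terms of quality of life.

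Much of this is fair as a limit on the finding. No printed figure is miscalculated; the fault is an unqualified statement that does not hold. The missing inputs alone would not be a finding, since a statistical analysis plan could supply them. But no such plan could make the sentence true, because it puts no bound on the difference. The conclusion also does not depend on one chosen rate or test: between 5% and 20%, neither test reaches 80% power for a doubling, and even a one-sided 5% test gives only 24% to 71% by the normal approximation.

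A narrower objection also stands. The Wald half-width is optimistic at a 5% rate, where only 50 × 0.05 = 2.5 infections per arm are expected. The average Newcombe half-width there is 10.3 points against 8.5; at 10, 15 and 20% it is 12.5, 14.2 and 15.5. Any quoted half-width should name its method.

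**Conclusion.** The concern holds. As a statement about SSI, the sentence is wrong as written. Without any assumption, no fixed sample size is adequate for a difference of unspecified size. With 50 per arm, a two-sided 5% test and control rates of 5 to 20%, the shortfall is large. A doubling would more likely than not be missed at control rates up to about 16% (chi-square) or 19% (Fisher). Reliable detection of a rise needs about 18 to 28 points, and at control rates of 10% or less no fall at all can be detected with 80% power.

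Because this is the only justification for the sample size, and it bears on the primary goal, it must be corrected. The finding concerns SSI only. It says nothing about power for quality of life, and large SSI differences remain detectable.

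**What to change.** Replace the sentence in Number of Subjects, item 2. If the investigators have a local SSI rate, they should state it with the chosen test and the matching detectable difference; that is shorter and better than a range. Otherwise, wording such as this would serve:

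> With 50 patients analysed per arm and a two-sided 5% test, the study has 80% power to detect an increase in SSI of about 18–21, 22–24, 24–26 or 26–28 percentage points if the control rate is 5, 10, 15 or 20% (assumed rates; chi-square to Fisher). It is not powered for smaller increases, nor for any decrease if the control rate is 10% or less. At 15% it has 80% power only for a fall of about 14 points or more by chi-square (not reached by Fisher), and at 20% for a fall of about 17–18 points or more. The expected 95% confidence interval half-width for the risk difference (Wald, both arms at the control rate) is about 9, 12, 14 or 16 points. Fewer patients analysed after removals would enlarge the detectable increases and the half-width.

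Optionally, commit to reporting the SSI risk difference with its 95% confidence interval, so that a non-significant result shows how large a difference it leaves open.

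The cost is the wording of one item and a less favourable stated power. Enrolment, visits and procedures are unaffected.

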### Study Procedures/ Design/Treatment Plan

1. Include study procedures/design/plan; include the sequence and timing of study procedures (distinguish research procedures from those that are part of routine care). Include study duration and number of study visits required.  
**Study will last 90 days. Patient's will be admitted to the hospital following surgery if the reconstruction takes place immediately following mastectomy. If the reconstruction does not occur at the same time as mastectomy, patients are not admitted. This is part of our routine care. Regardless, they will be evaluated on post operative day one. Following the initial post operative day one visit, patient's will be evaluated on a weekly basis for 90 days. Vitals will be taken at the visits, and routine physical examination (including evaluation for surgical site infection) will be performed. Patient reported outcomes will be obtained at these visits as well. We will also ask patients if they have been showering or not and if so how often. This will be documented. For example: patient evaluations will be as follows:**
  - One-month preoperative visit
  - Day of surgery
  - Post Operative Day one evaluation (In the hospital or clinic)
  - Clinic Visit 1: One week after surgery
  - Clinic Visit 2: Two weeks after surgery

**These visits will not differ from our routine care. At the conclusion of 90 days patients will receive a survey asking if drain care and the ability or inability to shower with drain tubes in place adversely affected their quality of life.**

2. Blinding, including justification for blinding or not blinding the trial. Describe unblinding procedures.  
**The study will not be blinded. Participants will be randomly assigned to treatment arm. Researchers and patients will know which arm they are assigned to.**
3. Justification of why participants will not receive routine care or will have current therapy stopped.  
**The goal of the study is to determine if there an effect on infection rate with allowing patients to begin showering 48 hours after surgery rather than waiting to shower until drains are removed. There is no definitive literature on this, and the care of surgical drains is ultimately decided by the surgeon. There is currently no defined standard of care regarding showering with surgical drains in place.**

4. Definition of treatment failure or participant removal criteria.  
**Removal criteria: failure to shower within 48 hours (experimental arm) or showering before surgical drain removal (Control group). Other removal criteria will be participants that have violated the post operative instructions in any way.**
5. Description of what happens to participants receiving therapy when study ends or if participation in the study ends prematurely.  
**At the end of the study or if patients choose to withdraw prematurely from the study, patients will continue to follow up at designated intervals for general postoperative monitoring.**
6. Include sub-studies or banking information (correlative/special studies)  

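### The only assessment expressly tied to quality of life is a recall survey at day 90, roughly ten weeks after drains come out; the weekly patient-reported outcomes are not said to measure it

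*Protocol*

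**What the plan says.** In Research Objectives/Background, the secondary goal is whether allowing showering affects quality of life, and the hypothesis is "improved quality of life in patients who are allowed to shower with drain tubes in place". The same section says where the loss is expected: "The recommendation not to shower until drain removal can present a significant challenge for patients resulting in distress and decreased quality of life". On duration it says: "Surgical drains can remain in place upwards of two to three weeks in the postoperative period". Potential Risks/Adverse Events, item 1, places the burden in the same period: "patients who will not be allowed to shower until drain tubes are removed will be allowed to sponge bath to help mitigate any discomfort".

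Study Procedures/ Design/Treatment Plan, item 1, describes two kinds of patient report. At the weekly visits, "Patient reported outcomes will be obtained at these visits as well"; no instrument, domain or objective is named for these. Then, "At the conclusion of 90 days patients will receive a survey asking if drain care and the ability or inability to shower" with drains in place had an adverse effect on quality of life. Of the two, only the second mentions quality of life. Item 2 of that section says that patients know their arm, and the Costs section makes the survey voluntary.

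Item 4 removes participants for "failure to shower within 48 hours (experimental arm) or showering before surgical drain removal (Control group"). Item 5 says of those who finish or withdraw early that "patients will continue to follow up at designated intervals for general postoperative monitoring".

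**The concern.** The two arms are managed differently only from the start of permitted showering until the drains come out. After that everyone may shower. An effect on quality of life should therefore be largest while drains are in, which is what the background section says. The one assessment named for that goal is taken long after the difference has ended.

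Three features weaken that survey as a between-arm measure:

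- It asks for recall and attribution. The patient is asked whether something affected her, not how she was at the time.
- Patients know their allocation, so the answer can be coloured by what they were told to do. By day 90 it can also be coloured by any infection that occurred during follow-up.
- It names drain care and showering together. Every patient has drain care; only showering differs by arm. If the two are asked as a single item, a positive answer cannot be assigned to showering.

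At stake is whether the secondary goal has usable data behind it. A quality-of-life score from the drain period cannot be obtained later, and no analysis plan can create one that was not collected.

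**Working it through.** The Protocol gives no figure for the interval between drain removal and the survey, so there is nothing to reproduce. The interval follows from its own dates.

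**Inputs**

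- Survey at day 90, and weekly visits for 90 days (Study Procedures/ Design/Treatment Plan, item 1).
- Drain removal at day *d* = 14 to 21 (Research Objectives/Background, item 2). The wording there is loose and no planned removal day is given, so *d* = 7 and *d* = 28 are added as assumptions to show the range.
- Showering allowed from day 2 in the experimental arm (48 hours; Research Objectives/Background and Number of Subjects). The removal criterion in item 4 words the 48-hour point differently, as a limit within which showering must happen. Those passages need reconciling; day 2 is used here as an assumption.

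**Recall interval** = 90 − *d*

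- *d* = 14: 90 − 14 = 76 days; 76/7 = 10.9 weeks
- *d* = 21: 90 − 21 = 69 days; 69/7 = 9.9 weeks
- Assumed *d* = 7: 83 days, 11.9 weeks
- Assumed *d* = 28: 62 days, 8.9 weeks

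**Time for which the arms differ** = *d* − 2

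- *d* = 14: 12 days; 12/90 = 13% of the study period
- *d* = 21: 19 days; 19/90 = 21%

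**Weekly visits available in that time**

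- All weekly visits by day 90: 90/7, rounded down, = 12 (days 7 to 84)
- Up to and including the removal day: 14/7 = 2 (days 7 and 14) or 21/7 = 3 (days 7, 14 and 21)

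**Contrast accumulated at the early visits**

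- Week 1: 7 − 2 = 5 days
- Week 2: 14 − 2 = 12 days, if drains are still in

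So two or three existing visits, at which patient-reported outcomes are already to be collected, fall in the period that the secondary goal concerns. The survey that names quality of life falls well outside it under every removal day tried. The size of any recall error cannot be estimated from the document.

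**The case against.** The strongest reply is that drain-period data are already planned. The Protocol has two goals. Infection is covered by physical examination, and showering frequency is asked about separately, so the natural use for weekly patient-reported outcomes is the quality-of-life goal. On that reading only a linking phrase is missing. This has force, and it rules out a stronger claim that a reader might infer: that the goal will be answered from remembered burden alone, or that no quality-of-life data will exist from the drain period. The document does not support that claim. It plans weekly patient-reported outcomes, does not exclude quality of life from them, and does not call the survey the sole or deciding measure. What survives is narrower: nothing in the text requires those outcomes to include quality of life.

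A second reply is that the choice of visit, the baseline adjustment and the analysis population belong in a statistical analysis plan, which is not shown. That is fair, and their absence is not the criticism. What is measured and when is fixed in the Protocol, and it is the stated timing and content of the survey that are at issue.

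Third, the survey asks specifically about showering with drains in, so it does target the right period. An attribution question at study end is legitimate but weaker. A general score at week 1 has its own limits: it reflects few days of contrast and also picks up early surgical recovery. Recovery affects both arms, so randomisation should balance it, though it adds noise.

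Finally, the removal criteria might be read as showing that the quality-of-life comparison will be biased by lost patients. The document does not say that data from removed participants are discarded or that collection stops. Those criteria touch every outcome and are a separate issue. They matter here only in that the added score should continue to be collected.

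**Conclusion.** The point holds as a weakness in how the secondary goal is measured, not as proof that the goal cannot be met. The only assessment expressly tied to quality of life is an unblinded recall-and-attribution survey about ten weeks after the arms stop differing. The weekly outcomes that could do better are not said to measure it.

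The size rests on the Protocol's loose two-to-three-week drain duration. An earlier or later removal moves the interval by about a week either way and does not change the conclusion. How much the weakness matters depends on what the weekly outcomes contain: if they already include a quality-of-life score, the remedy is a clarifying sentence and a stated comparison; if they do not, the drain-period evidence will be lost. The goal is secondary and the primary infection comparison is unaffected, so this should be corrected but does not threaten the trial as a whole.

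**What to change.** In Study Procedures/ Design/Treatment Plan, item 1:

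- State that the patient-reported outcomes include one short quality-of-life score, identical in both arms, with a recall period of at most one week, taken at the existing preoperative, week 1 and week 2 visits.
- Make the between-arm difference in that score at weeks 1 and 2 the secondary quality-of-life comparison, by randomised arm and adjusted for the preoperative score.
- Keep the day-90 survey as descriptive, with drain care and showering asked as separate items.

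In items 4 and 5, state that the score is still collected at routine visits from participants who meet the removal criteria, unless they withdraw consent.

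The cost is protocol wording and a few minutes at three visits that already take place; no visit is added and no showering instruction changes. Limits remain: reporting is still unblinded, week 1 reflects only about 5 days of contrast, and the contrast at week 2 shrinks if some drains are already out.

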**No compensation will be provided. Patients will be recruited for this study on a volunteer basis.**

### **Costs**

1. Detail costs of study procedures, drugs, biologics, or devices and identify who will cover the cost.  
**There is no attributed cost for study procedures. We will be implementing two treatment arms: showering after 48 hours post operative with JP drains in place vs showering after JP drain removal. Survey will be voluntary**

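### As described, the 90-day survey asks about drain care and showering together and only about harm, which dilutes the between-arm quality-of-life contrast and leaves improvement unrecorded

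*Protocol*

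**What the plan says.** The protocol's Research Objectives/Background section gives the secondary goal as "to evaluate whether allowing showering after a certain number of days post breast reconstruction has an effect on the quality of life of patients". The hypothesis in the same section includes "improved quality of life in patients who are allowed to shower with drain tubes in place".

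Study Procedures/Design/Treatment Plan, item 1, describes the measure: "At the conclusion of 90 days patients will receive a survey", and its content is "asking if drain care and the ability or inability to shower with drain tubes in place adversely affected their quality of life". The same item says of the clinic visits: "Patient reported outcomes will be obtained at these visits as well". It names no instrument or domain for these and does not link them to the quality-of-life goal.

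The Costs section states the randomised difference as "showering after 48 hours post operative with JP drains in place vs showering after JP drain removal" and makes the survey voluntary. On drain care, item 3 of the Study Procedures section says that "the care of surgical drains is ultimately decided by the surgeon". The number of survey items and the response scale are not given.

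**The concern.** This point is about what the survey asks, not when it is given.

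- **Two causes are joined.** All patients have drains to look after. Only permission to shower is randomised. A combined answer does not show which of the two a patient had in mind.
- **Only one direction is asked.** The stated content covers adverse effect. A patient for whom showering was a real help and a patient for whom it made no difference both fall under not adversely affected. The hypothesis, however, is worded as improvement.

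At stake is the secondary goal. If drain care troubles many patients in both arms, most will report an adverse effect whatever their shower assignment, and the arms will look alike. A null result could then mean that showering does not matter to quality of life, or only that the item could not pick it up. Combined answers cannot be separated at the analysis stage, so a statistical analysis plan cannot repair this.

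**Working it through.** **What the documents supply.** The only usable number is 50 patients per arm (Number of Subjects). That section calls the power adequate but gives no significance level, rates or effect size, and no figure for the survey. There is therefore no plan figure to reproduce. The flaw lies in the wording; the arithmetic below only shows how much it could matter.

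**Assumptions, none from the documents.** The item is answered yes or no, and yes means adversely affected by either cause. A share s is adversely affected by shower status: s_C in control, s_E in the showering arm. A share d is adversely affected by drain care, equal in both arms and independent of s. All 50 patients per arm respond. The test is a two-sided 5% comparison of two proportions.

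**Formulas.**
- P(yes) = 1 - (1-d)(1-s)
- Difference between arms = (1-d)(s_C - s_E)
- Power = Φ[(difference - 1.96·SE0)/SE1], where SE0 uses the pooled proportion and SE1 the two separate proportions

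**One case in full: s_C = 40%, s_E = 10%, d = 50%.**
- Control: 1 - 0.50 × 0.60 = 0.70
- Showering arm: 1 - 0.50 × 0.90 = 0.55
- Difference: 0.15, which is 0.50 × 0.30
- Pooled proportion 0.625; SE0 = √(2 × 0.625 × 0.375/50) = 0.0968
- SE1 = √((0.70 × 0.30 + 0.55 × 0.45)/50) = 0.0957
- Power = Φ[(0.15 - 1.96 × 0.0968)/0.0957] = Φ(-0.415) = 0.34

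**Range of assumed rates, 50 per arm.** Each pair has a true 30-point difference on a separate shower item (d = 0).

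| d | Difference (points) | Power, 60% v 30% | Power, 50% v 20% | Power, 40% v 10% |
|---|---|---|---|---|
| 0 | 30 | 0.87 | 0.89 | 0.95 |
| 25% | 22.5 | 0.63 | 0.62 | 0.62 |
| 50% | 15 | 0.39 | 0.36 | 0.34 |
| 75% | 7.5 | 0.19 | 0.17 | 0.16 |

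For 60% v 30%, the number needed per arm for 80% power rises from 42 with a separate item to 138 with a combined item at d = 50%.

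The loss is similar for all three pairs, so it is driven by d. The difference shrinks but keeps its sign, and it vanishes only if d reaches 100%.

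**Departures from the assumptions.** Fewer responders than 50 per arm, which is plausible for a voluntary survey, would lower every power figure. If drain-care burden overlaps with shower burden, the factor is no longer exactly 1-d. If drain-care burden differs between the arms, the combined answer mixes two arm effects.

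**The case against.** **The protocol describes a survey, not one question.** The sentence may only summarise its topics, and the form itself may already hold separate items or a graded scale. This stands as a limit: the point applies if the survey is run as the sentence describes. If the items are already separate, only the protocol sentence needs correcting.

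**Randomisation protects the comparison.** A reader might infer that the survey cannot show a benefit, or that a positive result could not be credited to showering. The documents do not support either reading. A burden that is equal in both arms cannot by itself create a difference between them. Fewer adverse answers in the showering arm would be evidence of relative benefit from the assigned policy. What is ambiguous is the individual answer and a null result.

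**The expected mechanism may be harm avoided.** Research Objectives/Background says that the shower restriction can cause distress and lower quality of life, and Potential Risks/Adverse Events lists reduced quality of life as a risk. Improvement can then be read as a comparison between arms, which an adverse-only item can partly capture. This weakens the complaint about direction but does not remove it: positive benefit still has no answer of its own.

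**Equal drain care is an inference.** The protocol leaves drain care to the surgeon and nowhere says that it is identical in the two arms. This is correct, and the factor 1-d depends on equal burden. Unequal burden would be a further reason for separate items.

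**Other patient-reported data are collected.** The visit-level outcomes may carry quality-of-life information. With no instrument, domain or link to the goal stated, they can be neither counted on nor dismissed.

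**Conclusion.** The point holds as a fault in the stated survey content. Run as one combined item, the survey cannot tie an individual answer to showering, loses between-arm contrast to drain-care burden, and cannot record the improvement that the protocol hypothesises. The consequence is reduced sensitivity and a null result that is hard to interpret.

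The size depends wholly on assumed rates. If drain care troubles a quarter of patients, the loss is moderate (power about 0.62-0.63 instead of 0.87-0.95). If it troubles three quarters, little sensitivity is left (0.16-0.19). The wording fault does not depend on these figures. It does depend on the survey following the protocol sentence, which the documents do not let a reader confirm. The change is worth making because it is cheap and cannot be made after the answers are in.

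**What to change.** Before any survey is given, state in Study Procedures item 1, and use in the survey, two separate items:

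- (a) the effect of drain care on quality of life;
- (b) the effect of being allowed, or not allowed, to shower while drains were in place.

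Give each a symmetric scale, for example much worse, worse, no effect, better, much better. Name item (b) as the survey's between-arm quality-of-life comparison. State also whether the patient-reported outcomes at visits serve the secondary goal and, if so, name the instrument.

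Cost: one extra survey item for each patient and an IRB amendment of the survey text. No extra visit or staff is needed.
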